3.6 CRITERIA FOR REMOVAL FROM PROTOCOL THERAPY AND OFF-STUDY CRITERIA

Prior to removal from study, effort must be made to have all subjects complete a safety visit approximately 30 days following the first follow-up evaluation on Day 56.

3.6.1 Criteria for Removal from Protocol Therapy

Patients will be taken off treatment for the following:

- Completion of treatment
- Grade 3 or 4 toxicity due to the vaccine, excluding those known events such as local injection site reactions, skin rash, pruritus, fatigue, fever and local adenopathy.
- Progression of disease
- Participant requests to be withdrawn from active therapy
- Investigator discretion
- Positive pregnancy test

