3.1.3 Protocol Stopping Rules

New subject enrollment to the protocol will be temporarily halted if any of the following conditions are met, and discussions will be had with the FDA or NIH IRB regarding protocol revisions if applicable:

- If one or more treatment-related death occurs due to vaccination, we will promptly discuss this with the NCI IRB and the FDA.
- Two or more patients develop a grade 3 or greater toxicity at any point in the study not attributable to disease progression (or circumstances unrelated to the study).
 - The following grade 3 reactions commonly associated with immunization **will not** be included in this protocol stopping rule:
 - Pruritus/itching: intense or widespread and interfering with ADL lasting <72 hours
 - Fatigue: severe fatigue interfering with ADL lasting < 72 hours
 - Fever: > 40.0°C for < 24 hours
 - Local lymphadenopathy lasting < 1 week
- If one of the first three patients (or 2 of the first 6 patients, or 3 of the first 9 patients, or 4 of the first 12 patients) develop grade 3 autoimmunity, that cannot be resolved to less than or equal to a grade 2 autoimmune toxicity within 10 days, or any grade 4 or greater autoimmune toxicity.

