3.3.2 Within 2 Days Prior to the 1st Vaccination (Day 0)

- Lymphocyte phenotyping (TBNK)
- Review of baseline symptoms
- Research samples as described in Section **5**

3.3.3 Within 2 Days Prior to Each Subsequent Vaccination (Days 14, 28, and 42 (± 5 days))

- Physical examination, including ECOG
- Vital signs
- CBC w/differential

- Acute Care Panel (sodium, potassium, chloride, bicarbonate, creatinine, glucose, BUN), Hepatic Panel (alkaline phosphatase, AST, ALT, total bilirubin, direct bilirubin), Mineral Panel (albumin, calcium, magnesium, phosphorus), Uric Acid, Creatinine Kinase, Lactate Dehydrogenase, Total Protein
- β -HCG pregnancy test (serum or urine) on all females of child-bearing potential
- Toxicity assessment, including a review of systems
- Research samples as described in Section **5**

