3.6.2 Off-Study Criteria

Patients will be taken off study for the following:

- Cells do not meet CoA requirements
- Completed study follow-up period
- Patient requests to be withdrawn from the study
- There is significant noncompliance
- Lost to follow-up
- Investigator discretion
- Progression of disease
- Death

All patients will be co-enrolled on the NCI SB companion protocol, 09-C-0161 (Follow up Protocol for Subjects Previously Enrolled in NCI Surgery Branch Studies). Patients who are taken off-study for progressive disease or study closure on the treatment protocol may be followed on protocol 09-C-0161.

Once a patient is taken off study, no further data can be collected.

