7.3 IND SPONSOR REPORTING CRITERIA

From the time the subject receives the investigational agent/intervention to the time of the second follow-up evaluation, the investigator must immediately report to the sponsor, using the mandatory MedWatch form 3500a or equivalent, any serious adverse event, whether or not considered drug related, including those listed in the protocol or investigator brochure and must include an assessment of whether there is a reasonable possibility that the drug caused the event. For serious adverse events that occur after the second follow-up evaluation, only those events that have an attribution of at least possibly related to the agent/intervention will be reported.

Required timing for reporting per the above guidelines:

- Deaths (except death due to progressive disease) must be reported via email within 24 hours. A complete report must be submitted within one business day.
- Other serious adverse events as well as deaths due to progressive disease must be reported within one business day

Events will be submitted to the Center for Cancer Research (CCR) at: [contact] and to the CCR PI and study coordinator.

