7.5 DATA AND SAFETY MONITORING PLAN

7.5.1 Principal Investigator/Research Team

The clinical research team will meet on a regular basis when patients are being actively treated on the trial to discuss each patient. Decisions about dose level enrollment and dose escalation if applicable will be made based on the toxicity data from prior patients.

All data will be collected in a timely manner and reviewed by the Principal Investigator. Adverse events will be reported as required above. Any safety concerns, new information that might affect either the ethical and or scientific conduct of the trial, or protocol deviations will be immediately reported to the IRB using iRIS.

The Principal Investigator will review adverse event and response data on each patient to ensure safety and data accuracy. The Principal Investigator will personally conduct or supervise the investigation and provide appropriate delegation of responsibilities to other members of the research staff.

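### The exemption in the removal-from-therapy rule (3.6.1) has no grade cap, so a grade 4 vaccine reaction of an exempted type would not require stopping the vaccine

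*Combined protocol and SAP*

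**What the plan says.** Section 3.6.1 lists the events for which a patient must come off treatment. The toxicity item reads "Grade 3 or 4 toxicity due to the vaccine, excluding those known events such as local injection site reactions, skin rash, pruritus, fatigue, fever" and then adds local adenopathy as a sixth example. The other items are completion, progression, participant request, investigator discretion and a positive pregnancy test.

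Section 3.1.3 contains a similar exemption for a different purpose, a temporary halt to new enrollment. Its general toxicity trigger is "Two or more patients develop a grade 3 or greater toxicity at any point in the study not attributable to disease progression". The carve-out from that trigger opens with "The following grade 3 reactions commonly associated with immunization" and names four types, each with a time limit: pruritus and fatigue (under 72 hours), fever (under 24 hours) and local lymphadenopathy (under 1 week).

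Other provisions bear on an individual patient's later doses:

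- Section 3.3.3 requires "Toxicity assessment, including a review of systems" before each of doses 2 to 4.
- Section 7.5.1 provides that "The clinical research team will meet on a regular basis when patients are being actively treated on the trial to discuss each patient" and that "The Principal Investigator will review adverse event and response data on each patient to ensure safety and data accuracy".
- Under section 7.3, "the investigator must immediately report to the sponsor" any serious adverse event, with a causality assessment.

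Grading follows CTCAE v5.0 (section 6.4). The scale itself is not reproduced.

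**The concern.** The sponsor chose a mandatory rule for severe vaccine toxicity and then exempted some familiar reactions. The exemption follows the phrase naming both grades and carries no limit of its own, so on its plain wording it reaches grade 4. A vaccine-caused grade 4 event of an exempted type would then leave the patient eligible for the next scheduled dose unless an investigator decided otherwise or the patient withdrew.

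The list is also open-ended, because the named reactions are given as examples, so the exemption is not strictly confined to the six.

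What is at stake is the protection of the individual patient. Autoimmune reactions, the product risk named in section 11.2, are not among the named exemptions.

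**Working it through.** The plan states no figure to reproduce. The check is a comparison of the two rules, a search for anything else that would stop a later dose, and a count of the doses involved.

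**1. The two exemptions side by side**

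| | 3.6.1 | 3.1.3 |
|---|---|---|
| Acts on | treatment of the affected patient | enrollment of new patients |
| Toxicity covered | grade 3 or 4, due to the vaccine | grade 3 or greater, not attributable to progression or unrelated circumstances |
| Grades exempted, as worded | 3 and 4 | 3 only |
| Types exempted | six named, list open | four named |
| Duration limit | none | one for each type |
| Patients needed to trigger | one | two |

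The rules serve different purposes, so they need not agree at grade 3, and a difference there is not an inconsistency. The relevant contrast is at grade 4. Section 3.1.3 counts a grade 4 reaction of any type. It draws the same line for autoimmunity: grade 3 is given 10 days to resolve, while any grade 4 or greater event counts at once. Section 3.6.1 draws no such line for its exempted types.

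**2. Following one grade 4 event of an exempted type**

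- Toxicity item in 3.6.1: not met, because the exclusion applies.
- Other items in 3.6.1: only investigator discretion lets the study team remove the patient because of the toxicity.
- Two-patient trigger in 3.1.3: the event counts, but a first case does not reach the threshold, and the halt would affect enrollment rather than this patient's doses.
- Assessment under 3.3.3: required, but no result is named that withholds the dose.
- Sections 7.5.1 and 7.3: these inform the decision without fixing it.
- The requirement in 2.1.1 that toxicities recover to grade 1 or less is an eligibility criterion tied to prior systemic therapy. It does not control later vaccine doses.

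**3. Doses resting on discretion**

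Four doses are planned, on days 0, 14, 28 and 42 (section 3.2). After dose k, 4 − k remain:

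- after dose 1: 4 − 1 = 3
- after dose 2: 4 − 2 = 2
- after dose 3: 4 − 3 = 1
- after dose 4: 4 − 4 = 0

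The maximum is 3 of 4, or 75%. This counts the doses affected if an event occurs; it does not measure how likely one is.

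**The case against.** The strongest objection is that no harm is shown. The point has force only if an exempted reaction has a grade 4 level. That depends on CTCAE v5.0, which the documents cite but do not reproduce, and where 3.1.3 grades such reactions it does so only at grade 3. This stands, and it is why the point is conditional and no frequency is claimed. For any type with no grade 4 level, the rewording changes nothing and costs nothing.

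A second argument is that a grade 4 reaction would not be a known event, because section 7.1.3 makes severity part of whether an event is expected. That reading is arguable. However, 7.1.3 defines an unexpected reaction for safety reporting, and 3.6.1 does not refer to it. A stopping rule should not depend on that inference.

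Third, discretion, the pre-dose assessment, review of each patient by the team and the principal investigator, and reporting to the sponsor make it unlikely that such an event would be ignored. That is fair and limits the weight of the point. Still, none of these makes removal mandatory. It can also be said that the plan gives a reason for the exemption, namely that the reactions are known. That explains exempting the types; it does not explain extending the exemption to grade 4.

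Finally, in refractory patients with limited life expectancy (section 10.5), continuing after a brief severe reaction may be a defensible clinical choice. It may be, but if it is intended, the protocol should say so.

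**Conclusion.** The concern holds as a wording gap in a patient-level safety rule, of modest weight. As written, the exemption in 3.6.1 covers two grades where that in 3.1.3 covers one, and no other provision requires removal or withholding of a dose after a grade 4 event of an exempted type. At most 3 of 4 planned doses would then rest on judgement.

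The conclusion rests on the plain reading of the bullet. Its practical importance depends on whether any exempted type can reach grade 4 under CTCAE v5.0, which the documents do not settle. The definition of the primary endpoint, the sample size and the design error rates are not touched.

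**What to change.** Reword the 3.6.1 toxicity bullet along these lines: *Any grade 4 toxicity due to the vaccine, or any grade 3 toxicity due to the vaccine other than known events such as* [the six types now listed]. This caps the exemption at grade 3 and changes nothing else; 3.1.3 stays as it is. Closing the list, or importing the duration limits from 3.1.3, would be optional clinical decisions. If the sponsor prefers discretion at grade 4, the protocol should state that and give the reason.

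The drafting cost is one bullet. The clinical cost falls on a patient with a vaccine-caused grade 4 event of an exempted type, perhaps a brief one, who would forfeit the remaining 3, 2 or 1 doses. That patient would stay in the analysis population of section 8.3, which requires only that the pulsed cells were given, and would be evaluable for response under 6.3.1 once disease is re-evaluated. The list in 3.6.2 headed "Patients will be taken off study for the following" does not include toxicity, so re-evaluation and response follow-up can continue. A patient counted in the response rate after fewer doses could in principle be less likely to respond; the documents give no basis for sizing that. No change to sample size, schedule or data collection is needed.

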3.6.2 Off-Study Criteria

Patients will be taken off study for the following:

- Cells do not meet CoA requirements
- Completed study follow-up period
- Patient requests to be withdrawn from the study
- There is significant noncompliance
- Lost to follow-up
- Investigator discretion
- Progression of disease
- Death

All patients will be co-enrolled on the NCI SB companion protocol, 09-C-0161 (Follow up Protocol for Subjects Previously Enrolled in NCI Surgery Branch Studies). Patients who are taken off-study for progressive disease or study closure on the treatment protocol may be followed on protocol 09-C-0161.

Once a patient is taken off study, no further data can be collected.

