6 DATA COLLECTION AND EVALUATION

6.1 DATA COLLECTION

The PI will be responsible for overseeing entry of data into an in-house password protected electronic system (C3D), and ensuring data accuracy, consistency and timeliness. The PI, associate investigators/research nurses and/or a contracted data manager will assist with the data management efforts. All data obtained during the conduct of the protocol will be kept in secure network drives or in approved alternative sites that comply with NIH security standards. Primary and final analyzed data will have identifiers so that research data can be attributed to an individual human subject participant. Data will be entered into the NCI CCR C3D database.

All adverse events (AEs), including clinically significant abnormal findings on laboratory evaluations, regardless of severity, will be followed until return to baseline or stabilization of event. Patients will be followed for adverse events from the time the patient receives the investigational agent/intervention to the time of the second follow-up evaluation, or until off-study, whichever comes first.

An abnormal laboratory value will be recorded in the database as an AE **only** if the laboratory abnormality is characterized by any of the following:

- Results in discontinuation from the study

- Is associated with clinical signs or symptoms
- Requires treatment or any other therapeutic intervention
- Is associated with death or another serious adverse event, including hospitalization.
- Is judged by the Investigator to be of significant clinical impact
- If any abnormal laboratory result is considered clinically significant, the investigator will provide details about the action taken with respect to the test drug and about the patient's outcome.

All AEs must be recorded on the AE case report form.

End of study procedures: Data will be stored according to HHS and FDA regulations, and NIH Intramural Records Retention Schedule as applicable.

Loss or destruction of data: Should we become aware that a major breach in our plan to protect subject confidentiality and trial data has occurred, the IRB will be notified.

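### Section 3.6.2 ends all data collection at off-study with no exception for the serious adverse events that Section 7.3 requires; the Section 3.6 safety visit narrows this conflict but does not remove it

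*Combined protocol and SAP*

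**What the plan says.** Section 3.6.2 lists the off-study reasons, among them progression, significant noncompliance, investigator discretion and cells that fail the certificate of analysis (CoA). It closes with the rule "Once a patient is taken off study, no further data can be collected".

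Section 7.3 sets the SAE duty: "From the time the subject receives the investigational agent/intervention to the time of the second follow-up evaluation, the investigator must immediately report" any SAE to the sponsor, related or not. It then continues the duty in narrower form: "For serious adverse events that occur after the second follow-up evaluation, only those events that have an attribution of at least possibly related" to the agent are reported. Neither sentence mentions off-study, and the second has no end date.

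Section 6.1 sets the general AE window from receipt of the agent "to the time of the second follow-up evaluation, or until off-study, whichever comes first".

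Two provisions bear on the gap:

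- Section 3.6, ahead of both lists of removal criteria, says: "Prior to removal from study, effort must be made to have all subjects complete a safety visit", timed at about 30 days after the Day 56 evaluation.
- Section 3.6.2 says "All patients will be co-enrolled on the NCI SB companion protocol, 09-C-0161", and then: "Patients who are taken off-study for progressive disease or study closure on the treatment protocol may be followed on protocol 09-C-0161".

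Progression is also on the Section 3.6.1 list, which opens "Patients will be taken off treatment for the following".

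**The concern.** A study team cannot obey 3.6.2 and 7.3 together, read as written, for a vaccinated patient who is off study and then has an SAE that 7.3 covers. Section 7.3 asks for a MedWatch form or equivalent with a causality assessment. That cannot be completed without data on the patient, and 3.6.2 says such data cannot be collected.

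Safety is a secondary objective (1.1.2), and Section 6.3.1 makes every patient evaluable for toxicity from the first vaccine. A patient removed early therefore stays in the safety denominator, possibly with a shorter period of observation than the others. The route is foreseeable: patients have refractory metastatic disease, the first scheduled imaging after baseline is at Day 56, and the second follow-up falls about a month later.

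**Working it through.** The plan states no figure for this point, so the check compares the sections and then counts visit days.

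**1. When each rule ends**

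| Rule | Section | Ends at |
|---|---|---|
| Any data collection | 3.6.2 | Off-study, without exception |
| AE follow-up | 6.1 | Second follow-up or off-study, whichever is earlier |
| All SAEs | 7.3 | Second follow-up; no off-study limit |
| At least possibly related SAEs | 7.3 | No end stated; no off-study limit |

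Sections 3.6.2 and 6.1 agree with each other. Section 7.3 agrees with neither.

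**2. Inputs for the day count**

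- Dose 4: Day 42 ± 5 (3.2)
- First follow-up with imaging: Day 56 ± 5 (3.4.1)
- Second follow-up: 1 month ± 5 days after the first (3.4.2). One month is taken as 30 days, which matches the 30 days in 3.6.

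**3. Removed for progression at the Day 56 scan, Section 3.6 visit missed**

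- Second follow-up: 56 + 30 = Day 86
- Window after dose 4 under 7.3: 86 − 42 = 44 days
- Window after dose 4 if collection stops at Day 56: 56 − 42 = 14 days
- Loss: 44 − 14 = 30 days; with the visit window, 30 − 5 = 25 to 30 + 5 = 35 days
- Range of the 14 days from the visit windows: 51 − 47 = 4 to 61 − 37 = 24 days

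**4. Same patient, Section 3.6 visit done before removal**

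The visit falls at about Day 86, which is also the second follow-up. The all-SAE window of 7.3 is then covered. Still in conflict are the at least possibly related SAEs after that visit, which 7.3 wants reported and for which 3.6.2 allows no data.

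**5. The two mitigating provisions**

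- Section 3.6 requires effort, not completion, and is not worded as an exception to the 3.6.2 bar.
- Co-enrolment on 09-C-0161 applies to all patients, but follow-up there is permissive. The sentence names only progression and study closure, and the documents do not show whether that protocol collects AEs.

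**6. CoA failure**

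A failure before any dose creates no conflict, because the 7.3 duty starts at first receipt of the agent. Product is formulated for each administration (11.2), so a failure after a first dose is possible. That patient meets the same conflict as any other vaccinated patient taken off study.

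**The case against.** The strongest reply is that Section 3.6 already reconciles the rules. It stands ahead of both removal lists, applies to all subjects, and places the safety visit before removal from study. Progression is listed under both off-treatment and off-study, and nothing says that off-study is immediate. The intended order may be to stop treatment, hold the visit, then remove the patient. This largely stands. A reader might infer that every patient who progresses loses 30 days of safety data, and the documents do not support that: the loss arises only when the visit is missed. What the reply does not cover is a missed visit and the related SAEs that come later.

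A second reply is that 7.3 governs reporting to the sponsor while 3.6.2 governs collection, and that 7.3 does not say it applies whatever the study status. The last part is correct: 7.3 is silent on study status, and an express override should not be read into it. But a report with a causality assessment needs data, so the silence leaves the conflict in place.

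Third, the off-study limit in 6.1 is an explicit choice, so it is not an error in itself that non-serious AEs go uncollected after removal. This stands. The case for aligning 6.1 is comparable observation time across the safety denominator.

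Fourth, 09-C-0161 may fill the gap. It may. Its content is not in these documents, so it can be counted neither as a gap nor as a remedy.

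**Conclusion.** The conflict between 3.6.2 and 7.3 is real, and it is one of stated rules. Its size depends on the Section 3.6 visit:

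- **Visit done:** little or none of the all-SAE window is lost, and the conflict is confined to later related SAEs.
- **Visit missed after removal at the Day 56 scan:** about 30 days are lost (25 to 35), leaving about 14 rather than 44 days after dose 4.

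These figures assume a 30-day month, four doses given on schedule, and removal on the day of the scan. The documents give no progression rate, no rate of missed visits and no rate of CoA failure, so the number of patients affected cannot be stated. Sample size, error rates and the primary endpoint are not affected.

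A reader might also infer a large loss of follow-up after a CoA failure. The documents do not support a figure: that would assume collection stops on the day of failure, whereas the Section 3.6 visit applies to all subjects. The point merits correction because it concerns required safety data and is cheap to fix.

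**What to change.** Reconcile Sections 3.6, 3.6.2, 6.1 and 7.3 with one safety exception in 3.6.2. For any vaccinated patient taken off study for a reason other than death, withdrawal of consent or loss to follow-up:

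- SAE collection and reporting continue as 7.3 requires, including at least possibly related SAEs after the second follow-up.
- AE collection continues to the second follow-up time point already named, by phone or e-mail where needed, as 3.4.2 allows.

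Align the off-study limit in 6.1 to match. The exception should not be confined to progression, because noncompliance and investigator discretion meet the same bar. It also covers a CoA failure after a first dose without separate wording.

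The cost is protocol text and one contact per affected patient, which Section 3.6 already intends. No treatment rule changes.
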